12.3. Reporting Period

For all AEs, the reporting period to Xeris begins from the subject providing informed consent, through the Follow-up Visit. All adverse events will be followed until resolution or the subject is medically stable.

12.4. Serious Adverse Events

An SAE is any untoward medical occurrence that at any dose:

- Results in death,
- Is life-threatening,
- Requires in-patient hospitalization or prolongation of existing hospitalization,
- Results in persistent or significant disability/incapacity, or
- Is a congenital anomaly/birth defect.

Medical and scientific judgment should be exercised in determining whether expedited reporting is appropriate in other situations, such as important medical events that may not be immediately life-threatening or result in death or hospitalization but may jeopardize the patient or may require intervention to prevent one of the other outcomes listed in the definition above. These should also usually be considered serious. Examples of such events are intensive treatment in an emergency room or at home for allergic bronchospasm or blood dyscrasias or convulsions which do not result in hospitalization.

12.5. Severity Assessment

On the AE eCRF, the Investigator will use the adjectives “mild,” “moderate,” or “severe” to describe the maximum intensity of the AE. These intensity grades are defined as follows in [Table 9](#).

Table 9 AE Severity Assessment

Mild	Does not interfere with subject’s usual function.
Moderate	Interferes to some extent (<50%) with subject’s usual function.
Severe	Interferes significantly (≥50%) with subject’s usual function.

The terms “serious” and “severe” are not synonymous. The term “severe” is often used to describe the intensity (severity) of a specific event. The event itself, however, may be of relatively minor medical significance. This is not the same as “serious,” which is based on

subject/event outcome or action criteria. Accordingly, a severe event is not necessarily a serious event.

12.6. Causality Assessment

The Investigator will answer “yes” or “no” to the following question when assessing causality between an adverse event to the study drug, where an answer of “yes” designates the event as related to study drug and a “no” designates the event as not related to study drug: “Is there a reasonable possibility that the drug caused the event?” A “reasonable possibility” means that there is evidence to suggest a causal relationship between the drug and the adverse event. The Investigator’s assessment of causality must be provided for all AEs. The Investigator must record the causal relationship in the eCRF, as appropriate, and report such an assessment in accordance with the serious adverse event reporting requirements, if applicable (Section 12.9).

12.7. Withdrawal Due to Adverse Events

Withdrawal due to AE should be distinguished from withdrawal due to insufficient response and recorded on the appropriate eCRF. When a subject withdraws due to an SAE, the SAE must be reported in accordance with the reporting requirements (see Section 12.9).

12.8. Eliciting Adverse Event Information and Reporting

The Investigator is to report all directly observed AEs and all AEs spontaneously reported by the study subject. Each study subject will be questioned about AEs. Each AE is to be assessed to determine if it meets the criteria for SAEs. If an SAE occurs, expedited reporting will follow the provisions of Section 12.9.

12.9. Serious Adverse Event Reporting Requirements

If an SAE occurs, Xeris is to be notified within 24 hours of awareness of the event by the Investigator. In particular, if the SAE is fatal or life-threatening, notification to Xeris must be made immediately, irrespective of the extent of available AE information. This time frame also applies to follow-up on previously forwarded SAE reports.

In the rare event that the Investigator does not become aware of the occurrence of an SAE immediately (e.g., a study subject initially seeks treatment elsewhere), the Investigator is to report the event within 24 hours after learning of the event and document the time of first awareness of the AE.

A death occurring during the study, during the per-protocol follow-up period, or within 30 days after stopping treatment with test drug must be reported to Xeris or its designee(s) immediately, whether or not it is considered treatment-related. Initial SAE reports must be followed by detailed descriptions. These should include copies of hospital case records and other documents when requested. Telephone and e-mail reports must be confirmed promptly either by facsimile or by overnight courier or mail.

Under 21 Code of Federal Regulations (CFR) 312.32(c), Xeris or its designee(s) is required to notify the FDA and all participating Investigators in an Investigational New Drug Application (IND) safety report (i.e., 7- or 15-day expedited report) of potentially serious risks from clinical

trials or any other source as soon as possible, but no later than 15 calendar days after the safety information is received and a determination is made that the information qualifies for reporting.

12.10. Non-Serious Adverse Event Reporting Requirements

All AEs will be reported on the AE page(s) of the eCRF. AEs should be reported using concise medical terminology on the eCRFs as well as on the form for collection of the SAE information.

12.11. AE Reporting Requirements to Regulatory Authorities

AE reporting by the Sponsor, including suspected serious unexpected adverse reactions, will be carried out in accordance with applicable regulations.

The Investigator must notify the Institutional Review Board (IRB)/Independent Ethics Committee (IEC) of the occurrence of any SAE, in writing, as soon as is practicable and in accordance with local regulations. A copy of this notification must be provided to Xeris or its designee.

In the event of an SAE that meets the criteria for expedited reporting, an SAE report will be prepared for submission to the FDA and any other applicable authorities by Xeris or its designee.

12.12. Pregnancy

The active pharmaceutical product in Xeris G-Pen is glucagon, which is in Pregnancy Category B. Female subjects of child bearing potential will be tested (rapid, urine) for pregnancy at the Screening Visit. Any subject found to be pregnant at the Screening Visit (Visit 1) will not be enrolled in the treatment phase. At both Treatment Visits and at the Follow-Up Visit (i.e., Visits 2, 3 and 4), pregnancy testing will be repeated. Any subject who is found to be pregnant at one of the Treatment Visits will be withdrawn from the study immediately and no further study treatments will be given. Pregnancy at the follow-up visit will be noted, but the visit will be completed. Any pregnancy in a subject who received at least one dose of study drug will be followed until resolution (i.e., birth or voluntary or spontaneous termination of the pregnancy). Any pregnancy outcome that meets the criteria for an SAE will be reported as an SAE.

12.13. Subject Monitoring

Subjects will be monitored for AEs throughout the study by the study unit staff. The principal Investigator or designated sub-Investigator will be on site for drug administration and until 3 hours after administration of study drug to the last subject. The principal Investigator or designated sub-Investigator will also be on call for the remainder of the treatment visit. If necessary, a physician, either at the study site or in a nearby hospital, will administer treatment for any AEs.

Safety parameters, including laboratory results and ECGs, will be assessed by the principal Investigator or his delegate using the site's criteria for clinical laboratory and ECG acceptance ranges as suggested guidelines in making the medical assessment.

Scheduled safety measurements will be repeated according to appropriate SOPs or upon request from a physician. Any abnormal repeated measurement will be evaluated by a physician and repeated if judged necessary. Further action may be taken on the physician's request.

Subjects will be advised to notify their health care professionals (e.g., physician, dentist, and/or pharmacist) that they are participating in a clinical research study of a drug called synthetic Glucagon Injection before taking any medicines or undergoing any medical procedure.

13. DATA ANALYSIS AND STATISTICAL METHODS

13.1. General Approach

Detailed methodology for descriptive and inferential statistical analyses of the data collected in the XSGP-304 study will be documented in the statistical analysis plan (SAP). The SAP will be prepared by the Sponsor's contract research organization (CRO) and agreed upon by the Sponsor. The SAP will be finalized and approved by signature and dates prior to locking the database. Additional graphical representations of the results may be produced after review of the data (post hoc). The SAP will take precedence over the protocol. The primary objective of the study is to test whether G-Pen is no worse than the GlucaGen Hypokit for injection in terms of hypoglycemia relief. Any major modifications of the definition of the Primary Endpoint or analysis will be reflected in a protocol amendment.

13.2. Sample Size Calculation

For the primary endpoint analysis, a failure is recorded if the subject's plasma glucose fails to reach a concentration >70 mg/dL (>3.88 mmol/L) *and* fails to increase by at least 20.0 mg/dL (1.11 mmol/L) within 30 minutes of the decision to administer the dose of glucagon. The determination of a constant clinically non-inferior margin for the cure rate difference is generally difficult in practice for a number of reasons. To alleviate this concern, it has been recommended to use an Odds Ratio of cure rates because the corresponding clinically non-inferior margin on the difference scale is getting small when the underlying cure rate becomes large and close to 1 [Lui and Chang(a)]. In this study, it is expected that the recovery (cure rate) will be high and approaching 100%. Since this is a cross-over design and each subject will serve as his/her control, power is improved.

The sample size was derived for 80% power of detecting non-inferiority with respect to the Odds Ratio of subject recovery rates at an alpha of 0.025 under a cross-over design [Lui and Chang(b)] Based on an underlying Odds Ratio of 1.0, and rates of 0.20 versus 0.25, 111 subjects are required for the study. With an anticipated 10% drop-out rate, the total sample size for the study is 122 randomized subjects.

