After 180 minutes posttreatment, subjects will resume insulin pump therapy, if applicable, and will be given a meal. Subject may be discharged after 180 minutes posttreatment if their plasma glucose is > 100 mg/dL (5.56 mmol/L) and if medically stable. At the Investigator’s discretion, subjects’ prescribed insulin regimen can be restarted, or the meal can be given sooner, but not earlier than 90 minutes post-glucagon treatment, to prevent hyperglycemia or rebound hypoglycemia.

After a wash-out period of 7 to 28 days, subjects will return to the CRC and the study procedures will be repeated with each subject crossed over to the other treatment. After study-related procedures are performed on each of the treatment days, subjects will be discharged. A Follow-Up Visit will be

XSGP-304 Clinical Protocol
G-Pen (glucagon injection)

	
conducted 2 to 7 days after administration of the final dose of study drug as a safety check.
 
Tolerability will be assessed by comparing AE reports between the G-Pen and GlucaGen Hypokit treatment groups. In addition, at the end of each treatment period the subjects will complete questionnaires to assess injection site discomfort, and the Investigator will use a modified Draize scale to evaluate the injection sites after each administration.

Data management and statistical analysis:	
Data will be entered into an electronic Case Report Form (eCRF) by the study site personnel. Data will be monitored at on-site visits by Xeris personnel or by a contract research organization (CRO) delegated by Xeris. A stand-alone Statistical Analysis Plan (SAP) will be written to detail all protocol specified analyses. The SAP will take precedence over the protocol. The primary endpoint will be analyzed using an exact test procedure based on the conditional distribution for a maximum clinically acceptable non-inferior margin of $\leq 5\%$.

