Sample Size Determination:	
For the primary analysis, a failure is recorded if the subject's plasma glucose fails to reach a concentration >70 mg/dL (>3.88 mmol/L) and fails to increase by at least 20.0 mg/dL (1.11 mmol/L) within 30 minutes of the decision to administer the dose of glucagon. The determination of a constant clinically non-inferior margin for the cure rate difference is generally difficult in practice for a number of reasons. To alleviate this concern, it has been recommended to use an Odds Ratio of success rates for estimation because the corresponding clinically non-inferior margin on the difference scale is getting small when the underlying success rate becomes large and close to 1. In this study, it is expected that the subject's recovery (success rate) will be high and approaching 100%. Since this is a cross-over design and each subject will serve as his/her control, power is improved.
 
The sample size was derived for 80% power of detecting non-inferiority with respect to the Odds Ratio of subject recovery rates at an alpha of 0.025 under a cross-over design. Based on an underlying Odds Ratio of 1.0, and failure rates of 0.2 versus 0.25, 111 subjects are required for the study. With an anticipated 10% drop-out rate, the total sample size for the study is 122 randomized subjects.

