13.3. Primary Endpoint

The primary endpoint comparison will be performed using both the Intention to Treat (ITT) and the per-protocol (PP) populations. The evaluable set for the PP population will be defined as all randomized subjects who, during both study periods, successfully complete the insulin induction procedure, fulfill the criteria for having achieved a hypoglycemic steady state, and successfully receive a dose of both study drugs (G-Pen followed by GlucaGen Hypokit, or GlucaGen Hypokit followed by G-Pen). For analysis of the primary endpoint, a failure for the study treatment (G Pen or GlucaGen Hypokit) will be recorded if the increase in plasma glucose remains < 20 mg/dL (< 1.11 mmol/L) throughout the 0- to 30-minute period from injection of study drug, while a success is defined as an increase in plasma glucose ≥ 20 mg/dL (≥ 1.11 mmol/L) in subjects from a state of insulin-induced hypoglycemia within the 0- to 30-minute period from injection of study drug.

Non-inferiority will be established based on the calculated 95% confidence interval for the difference in failure rates between G-Pen and GlucaGen Hypokit. Non-inferiority will be declared if the upper limit of the 95% confidence interval for the difference in failure rates is $\leq 5\%$; where the absolute failure rate of G-Pen treatment is $\leq 5\%$.

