4.2 Sample Size Determination

For the primary objective, a failure is recorded if the subject’s plasma glucose fails to rise above 70.0 mg/dL (3.88 mmol/L) and fails to increase by at least 20.0 mg/dL (1.11 mmol/L) within 30 minutes of the decision to administer the dose of glucagon.

In this study, it is expected that the recovery (cure rate) will be high and approaching 100%. Since this is a cross-over design and each subject will serve as his/her control, power is improved.

The sample size was derived for 80% power of detecting non-inferiority with respect to the Odds Ratio of subject recovery rates at an alpha of 0.025 under a cross-over design. Based on an underlying Odds Ratio of 1.0, and rates of 0.20 versus 0.25, 111 subjects are required for the study. With an anticipated 10% drop-out rate, the total sample size for the study is 122 randomized subjects.

If there are subjects who are enrolled, but fail to be randomized, compensatory enrollment may be utilized to achieve at least 122 subjects who are randomized for the study. Once a subject is randomized, the subject will be analyzed for the study.

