5.1.1 Intent-to-Treat Population (ITT)

The Intent-to-Treat (ITT) population is defined as all subjects randomized. A subject’s randomized treatment will be used for analysis regardless of the actual treatment received. ITT population will be used for all summaries except safety/tolerability and disposition (where Enrolled population will be used). Primary endpoint comparison and secondary efficacy analysis will be performed for ITT, mITT and PP populations.

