6.5 Analysis of Primary Endpoint

The primary endpoint analysis will be based on the risk difference in rates of failing to achieve Positive Plasma Glucose Response (PGR) of G-Pen versus GlucaGen Hypokit and a 95% CI will be calculated. Non-inferiority will be declared if the upper limit of the 95% confidence interval for the difference in failure rates is $\leq 5\%$; where the absolute failure rate of G-Pen treatment is $\leq 5\%$. This analysis will be repeated for ITT, mITT and PP populations.

Subjects who are missing the primary endpoint for a study treatment will be considered as having a failure in the primary analysis for that treatment administration. This imputation will be conducted for both the ITT and the mITT populations. If a subject received the same two treatment administrations for both periods (Period 1 and Period 2), only the visit with the planned treatment received will be included in the primary analysis and the subject will be considered a failure in the primary analysis for the for unreceived treatment administration (ITT, mITT). For all other analyses, data will be included for only the planned treatment received in those analyses.

A sensitivity analysis will be performed for where all missing data will be considered a success and the same analysis as above completed.

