APPENDIX 2: CODE FRAGMENTS

Risk difference test for binary response

```
Proc Freq data = <Data> order=data;  
    weight Count / ZEROS;  
    tables <Treatment>*<Response> / riskdiff;  
    output out = <Out> riskdiff;  
run;
```

Mixed model

```
ods output lsmeans(match_all) = <Out_LSmean>  
           Diffs(match_all) = <Out_Diffs>;  
Proc Mixed data=<Data>;  
    class <Treatment> <Period> <Subject>;  
    model <Value> = <Treatment> <Period> <Treatment>*<Period>;  
    random <Subject> / Type = un;  
    lsmeans <Treatment> / cl DIFF;  
run;
```

Time-to-Event

```
ods output means=<Out_Means> HomTests=<Out_Test>;  
proc lifetest data=<Data>;  
    time <Time>;  
    strata <Treatment>;  
run;
```

Study Drug Assignment

```
proc freq data=<Data>;  
    tables <Treatment>/ BINOMIAL (p=0.50) alpha=0.05;  
    output out=<Out> Binominal;  
    weight count;  
run;
```

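### The stated 80% power belongs to an odds-ratio test at 0.20 versus 0.25, not to the 5-point risk-difference rule that decides the trial, and it ignores missing-as-failure in ITT

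*Protocol*

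**What the plan says.** **Sizing.** Protocol 13.2 and SAP 4.2 use the odds ratio of recovery rates, alpha 0.025 and 80% power: "Based on an underlying Odds Ratio of 1.0, and rates of 0.20 versus 0.25, 111 subjects are required for the study". Only the synopsis says what kind of rates these are: "failure rates of 0.2 versus 0.25, 111 subjects are required for the study". A 10% dropout allowance takes 111 to 122 randomized. The same sections expect recovery close to 100%. They start the 30-minute window at the decision to dose ("within 30 minutes of the decision to administer the dose of glucagon"), whereas the endpoint definitions in Protocol 5.3.1 and SAP 3.3.1 start it at injection.

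**Decision.** Protocol 13.3 and SAP 6.5 declare non-inferiority if the upper limit of the 95% confidence interval for the difference in failure rates is at most 5%, followed by the clause "where the absolute failure rate of G-Pen treatment is" at most 5%.

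**Method.** The synopsis describes "an exact test procedure based on the conditional distribution for a maximum clinically acceptable non-inferior margin" of at most 5%. The SAP's sample code is "tables <Treatment>*<Response> / riskdiff", with no term for pairing within subject.

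**Analysis set.** SAP 5.1.1: "The Intent-to-Treat (ITT) population is defined as all subjects randomized". SAP 6.5: "Subjects who are missing the primary endpoint for a study treatment will be considered as having a failure in the primary analysis", applied to ITT and mITT. A sensitivity analysis counts missing data as success.

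**The concern.** A reader of either document would take 80% as the probability that the declared rule succeeds. It was derived for another test, on another scale, at failure rates the same section does not expect, with another start to the 30-minute window, and with dropouts removed rather than counted as failures. Protocol 13.2 says a constant margin on the difference scale is hard to justify and gives that as the reason for using the odds ratio. Protocol 13.3 then decides on a constant 5-point difference.

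The inputs also disagree with each other. Rates of 0.20 and 0.25, if they are the true rates of the two arms, do not give an odds ratio of 1.0.

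What is at stake is knowing what the trial can deliver. The ITT analysis is the most exposed, because ordinary dropout could decide it even if both drugs always work.

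**Working it through.** **1. Can 111 be rebuilt?** Not from the stated inputs, because the odds-ratio margin and the within-subject correlation are missing. Suppose 0.20 versus 0.25 defines the margin:

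- Odds are 0.20/0.80 = 0.250 and 0.25/0.75 = 0.333, so the ratio is 0.75 (or 1.33 inverted), and ln(0.75)² = 0.0828.
- For a crossover with true odds ratio 1, N = 2(1.960 + 0.842)² / (q × 0.0828) ≈ 189.7/q. Here q is the probability that a subject fails on one named drug only.
- With independent periods, q = p(1 − p). At p = 0.20, q = 0.16 and N = 1,186. At p = 0.25, q = 0.1875 and N = 1,012.
- q cannot exceed the failure rate. At these upper limits, 0.20 and 0.25, N is still about 950 and 760.

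Working backwards from N = 111, (ln margin)² = 15.70/(111q). This gives a margin of about 2.6 at q = 0.16 and 2.1 at q = 0.25. An exact conditional test with 55 per sequence reaches 81% at a margin of 2.5 with 45% of subjects discordant. So 111 is attainable, but only with a margin that neither document states.

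**2. The deciding rule at the planning rate (20% failure on both drugs, n = 111).** Read as pass/fail, the cap allows 5 G-Pen failures (5/111 = 4.5%; 6/111 = 5.4%). P(X ≤ 5 | 111, 0.20) = 2.7 × 10⁻⁶. Without the cap, SE = √[2 × 0.20 × 0.80 × (1 − ρ)/111] and power = Φ(0.05/SE − 1.960):

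- ρ = 0: SE = 0.0537, power 15%.
- ρ = 0.5: SE = 0.0380, power 26%.

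**3. The deciding rule at low failure rates (completers, n = 111).** These powers come from full enumeration with equal true rates, independent periods and the cap applied. The unpaired Wald interval is what the SAP's sample code produces by default. The paired (Tango) score interval is an illustrative alternative that neither document names.

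| True failure rate | Unpaired Wald | Paired score |
|---|---|---|
| 0.5% | 98% | 90% |
| 1% | 92% | 76% |
| 2% | 77% | 57% |

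At 1% failure the paired-score power rises to 82% at correlation 0.2 and 90% at 0.5, crossing 80% near 0.15. The Wald rule falls to 80% at a failure rate of about 1.8%.

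**4. ITT with missing counted as failure (n = 122, no drug failures).** Assume each dropout misses one treatment, equally likely to be either drug.

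| Dropout | Unpaired Wald | Paired score |
|---|---|---|
| 2% | 94% | 74% |
| 5% | 71% | 54% |
| 10% | 43.5% | 34% |

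Dropping the cap at 10% dropout changes this only to 46.7% and 35.6%.

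The plan's own allowance is 122 − 111 = 11 dropouts. If 6 miss G-Pen and 5 miss GlucaGen, the rates are 4.92% and 4.10%. The Wald upper limit is 0.82 + 1.960 × 2.66 = 6.03% and the score limit is 6.88%, so both fail. If the split is 5 and 6, the limits are 4.39% (pass) and 5.11% (fail).

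The pattern of missing data matters more than the interval. If 10% of subjects miss both periods, Wald power is about 1%. With equal failures on both drugs the limit is 4.98% at 5 such subjects and 5.43% at 6, and P(X ≤ 5 | 122, 0.10) = 1.4%.

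**The case against.** The strongest reply is that no arithmetic has been shown to be wrong. The margin may sit in the cited methods paper, 111 can be reached with a margin of 2.1 to 2.6, and the plan expects failure far below 20%. At 1% failure or less the coded interval gives 92% to 98% for completers, above the stated 80%. This stands. The near-zero and 15% to 26% figures, and the 760 to 1,186 subjects, describe readings of the planning rates, not the trial's likely performance.

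The score interval is the reviewer's choice, and SAP 6.1 lets the actual code differ from the samples. That also stands, and it is a reason to name the method.

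The ITT figures depend on an assumed pattern. Ten percent of 122 is 12.2 dropouts on average. With exactly 11 one-period dropouts allotted at random, the Wald rule passes when at most 5 miss G-Pen, which is 50%. The score rule needs at most 4, which is 562/2,048 = 27%. The 111 are meant to be evaluable in both periods, much like the per-protocol set, which excludes these subjects. There is also a missing-as-success sensitivity analysis. However, neither document makes per-protocol decisive, and SAP 6.5 puts missing-as-failure in the primary analysis.

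The difference in clock does not enter the calculation of 111. It shows only that the sizing text describes a different endpoint. SAP precedence over the protocol does not help either, because SAP 4.2 repeats the odds-ratio basis.

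**Conclusion.** The concern holds. The 80% is not a property of the deciding rule, the endpoint's clock or the ITT set, and 111 cannot be reproduced from what is written.

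This does not establish that 111 completers are too few. At 1% failure, power is above or below 80% depending on the interval and the correlation. With the coded Wald interval and independent periods, it is at least about 80% for failure rates up to about 1.8%.

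The ITT exposure is the more serious part. At the plan's own dropout allowance, with no drug failures, the chance of passing is roughly 27% to 50% if each dropout misses one treatment, depending on the interval and on how dropout is modelled. It is about 1% if 10% miss both. One subject's allocation, or the choice of interval, can then decide the result. These figures rest on equal true failure rates, the stated missingness patterns and, except where noted, the 5% clause acting as a cap.

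**What to change.** In Protocol 13.2, the synopsis and SAP 4.2, replace the odds-ratio basis and the 0.20/0.25 rates with the inputs of the rule actually used:

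- the 5-point limit on the difference in failure rates;
- whether the 5% G-Pen clause is a success criterion;
- one named confidence-interval method, reconciled with the exact test in the synopsis and the code in SAP Appendix 2;
- the assumed failure rate for each drug and the within-subject correlation;
- the 30-minute window counted from injection.

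Then report the power the planned N delivers, once for 111 completers and once for the 122-subject ITT set with missing counted as failure, stating the assumed dropout pattern. If the sponsor wants a record of how 111 was first chosen, the odds-ratio margin and correlation can be given as history, but not as the power of the trial. The figures above are illustrations, not replacement text.

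The cost is wording in both documents and one recalculation. The stated power becomes conditional on failure rate, correlation and dropout, and will look less favourable for ITT. The fix does not itself require a change to N.

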	
 6. Time to administer study drug from a decision to dose. 7. Pharmacodynamic (PD) characteristics of mean plasma glucose concentration (0 to 90 minutes post-dose), maximum observed concentration (C_{max}), time to maximum observed concentration (t_{max}), area under the concentration versus time curve from time 0 to 90 minutes ($AUC_{(0-90)}$), and area under the concentration versus time curve from time 0 to 180 minutes ($AUC_{(0-180)}$). 8. Time to (a) initial relief and (b) complete resolution of autonomic and neuroglycopenic symptoms of hypoglycemia from a decision to dose. 9. Time to resolution of the overall feeling of hypoglycemia from a decision to dose. 10. Safety endpoints, including: adverse event (AE)/serious adverse event (SAE) rates, and changes in vital signs, laboratory variables, and physical exam/electrocardiogram (ECG) findings. 11. Tolerability endpoints, including: Draize scale scores for injection site erythema and edema as assessed by the investigator, and injection site discomfort and duration as assessed by subject questionnaire responses.
Study design:	This is a multi-center, randomized, active-controlled, single-blind, two-way crossover efficacy and safety inpatient study in adult subjects with T1D. The study will involve two daytime visits at a clinical research center (CRC) or comparable setting, scheduled 7 to 28 days apart. Subjects will be randomly assigned to receive G-Pen glucagon 1 mg during one period and GlucaGen Hypokit 1 mg during the other period.
Study location:	Approximately 8 clinical research centers in North America and Europe.
Study duration:	The estimated duration of study participation for each individual subject is approximately 4 weeks. The estimated duration of the entire study is 8 months.
Sample size:	It is anticipated that approximately 200 subjects will be screened for this study to achieve 122 randomized subjects and a goal of 111 subjects who are evaluable for treatment both periods.
Subjects:	The study will include male and female subjects with T1D between the ages of 18 and 75 years, inclusive, at Screening.

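### At the stated 10% drop-out, 122 randomized subjects give about 110 evaluable in both periods, not the stated 111; the three figures need a small text correction

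*Protocol*

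**What the plan says.** Three numbers appear together in three places: the Protocol synopsis (Sample Size Determination), Protocol 13.2 and SAP 4.2.

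- **Required number.** Protocol 13.2 says "111 subjects are required for the study". This comes from a calculation with 80% power "at an alpha of 0.025 under a cross-over design".
- **Drop-out and randomized number.** The next sentence of Protocol 13.2 is "With an anticipated 10% drop-out rate, the total sample size for the study is 122 randomized subjects". SAP 4.2 carries the same sentence.
- **What 111 counts.** The Sample size row of the synopsis plans screening "to achieve 122 randomized subjects and a goal of 111 subjects who are evaluable for treatment both periods". So 122 is the number before loss and 111 the number after it.

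None of these places says how 111 was inflated to 122.

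Two other provisions bear on the point. Protocol 9.1 and SAP 4.2 allow compensatory enrolment for subjects who are enrolled but not randomized, to reach at least 122 randomized. SAP 6.5 deals with missing outcomes in the ITT and mITT sets: "Subjects who are missing the primary endpoint for a study treatment will be considered as having a failure in the primary analysis".

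**The concern.** A drop-out rate is ordinarily a share of those randomized. On that reading, the evaluable number is the randomized number times one minus the rate, and the stated size should return at least 111. It does not. The plan therefore names a required evaluable number that its own size and its own expected loss do not deliver.

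What is at stake is the internal consistency of the sample-size statement, and a very small amount of power in the analysis that needs both periods. The per-protocol set is one of the populations for the primary comparison (Protocol 13.3; SAP 5.1.3 and 6.5), so the both-period count is a number that the plan uses. The SAP, which supersedes the protocol's statistical considerations, carries the same mismatch.

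**Working it through.** **Inputs.** Required evaluable n = 111 (Protocol 13.2; defined as evaluable in both periods in the synopsis). Drop-out d = 10% and randomized N = 122 (synopsis, Protocol 13.2, SAP 4.2). Power 80% and alpha 0.025 (Protocol 13.2). The sidedness of alpha is not stated; I take it as one-sided because the test is for non-inferiority.

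**1. Reproducing the plan's 122.** Adding 10% to the evaluable number:

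n × (1 + d) = 111 × 1.1 = 122.1, which rounds to 122.

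This matches the stated figure.

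**2. Inflating for a loss from those randomized.**

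n / (1 − d) = 111 / 0.9 = 123.3, rounded up to 124.

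Check: 123 × 0.9 = 110.7, still short of 111; 124 × 0.9 = 111.6, enough.

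**3. What 122 delivers at 10% loss.**

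122 × 0.9 = 109.8, about 110.

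Shortfall: 111 − 109.8 = 1.2 expected evaluable subjects, or 124 − 122 = 2 randomized subjects.

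**4. The loss at which 122 gives 111.**

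(122 − 111) / 122 = 11 / 122 = 9.0%. At 9%, 122 × 0.91 = 111.02.

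**5. Effect on power.** I take 111 as correct for 80% power and scale by a normal approximation:

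power = Φ[(1.960 + 0.842) × √(m / 111) − 1.960], where m is the evaluable number.

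| Evaluable m | Approximate power |
|---|---|
| 111 | 80% |
| 110 | 79.6% |
| 109.8 | 79.6% |
| 109 | 79.3% |

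The loss at the expected 109.8 is about 0.4 percentage points.

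**6. What was not checked.** The 111 itself cannot be re-derived. The odds-ratio margin and the within-subject correlation are not given, and it is unclear how the rates of 0.20 and 0.25 enter the calculation. Steps 1 to 4 do not depend on this; step 5 takes 111 as given.

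**The case against.** The strongest reply is that this is within the tolerance of any planning calculation. The 10% is a forecast and the synopsis calls 111 a goal. A loss of 9.0% instead of 10% closes the gap. With 111 not verifiable from the documents, a discrepancy of 1.2 subjects says little about whether the trial is adequately sized. All of this stands, and it limits the point to a correction of wording. It does not make the figures agree: Protocol 13.2 and SAP 4.2 state 111 as required, without qualification.

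A second reply is that 122 is a floor, since compensatory enrolment aims for at least that many. That provision covers subjects who fail to be randomized. The documents do not provide for replacing subjects lost after randomization, which is the loss that the 10% must cover. The floor would permit two more subjects, but the plan does not call for them.

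A third reply is that drop-out does not shrink the ITT analysis. This is right. SAP 5.1.1 defines ITT as all randomized subjects, and SAP 6.5 counts a missing primary endpoint as a failure. All 122 stay in that comparison, so the shortfall concerns the evaluable and per-protocol count. Imputed failures can affect the ITT result, but that is a separate matter.

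Finally, a reader might infer that the documents show a formula error, with 111 multiplied by 1.1 where division by 0.9 was meant. The match at 122.1 makes this likely, but no formula is printed. If the 10% was meant as an allowance added to 111, 122 is the correct rounded result and the term drop-out rate is what misleads.

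**Conclusion.** The point holds as a small inconsistency. If the 10% is a share of those randomized, 122 randomized subjects are expected to leave 109.8 evaluable in both periods, against a stated 111; reaching 111 at that loss would take 124. The gap is about 1.2 evaluable subjects. By normal approximation, and if 111 is correct for 80% power at one-sided 0.025, power is roughly 79.6%.

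The arithmetic needs only the three printed figures and the ordinary meaning of drop-out rate. The explanation, that 10% was added to 111, is an inference from the match with 122.1.

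A reader might go further and conclude that the trial is materially undersized or must randomize more subjects. The documents do not support that. The power loss is a fraction of a percentage point, the ITT set keeps all randomized subjects, and a loss one point below the forecast removes the gap. Nor does this check say whether 111 is itself the right number.

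**What to change.** Make the three figures agree, in one of two ways.

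- **Preferred:** restate the anticipated drop-out as about 9% in the synopsis (Sample Size Determination), Protocol 13.2 and SAP 4.2. This leaves both 111 and 122 unchanged and consistent.
- **Alternative:** keep 10% and state that about 110 evaluable subjects are expected, with power slightly under 80%. The synopsis goal of 111 should then be brought into line. The sentence requiring 111 needs the power statement beside it; otherwise the text would still require more evaluable subjects than it expects.

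It would also help to state the inflation formula in a few words. The cost is a text edit in the protocol and the SAP. No extra enrolment, procedure or change of analysis is needed.
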